Current training methods include preventive strategies focused on modifying neuromuscular and biomechanical risk factors^{31,32} using non-football-specific tasks such as eccentric exercises or verbal or visual *feedback* combined with plyometric, *core*, balance, resistance or trunk strengthening exercises. These could be the most effective to positively modify the screening, identification and correction of dangerous movement patterns^{1,26} such as DKV during jump-landing tasks^{14,21,31,33,34}. However, no uniform criteria have been established to design a precise intervention protocol, with specific tasks linked to women's football, nor has it been proposed to optimize current programs despite having a high number of injuries associated with DKV^{33,34}. On the other hand, there is no consensus or unification on the establishment of defined parameters regarding the effective dosage of a specific training program, since there is great heterogeneity in terms of the doses and times of the scheduled exercises. These preventive programs are effective in the short term, but it is not equally confirmed whether they produce positive effects in the long term³¹. Current evidence reports that the implementation of specific preventive programs according to the sport practiced is imperative to reduce the incidence of ACL injuries. In addition, in terms of exercise effectiveness, it suggests a 51% reduction in these injuries^{2,20,35,36}.

Based on the review recently published in the journal *Fisioterapia*¹⁶, we proceed to propose, as a continuation of the current research process, an exercise protocol, as well as its dosage in female footballers with DKV, in order to reduce the risk of ACL injuries.

OBJECTIVES AND HYPOTHESES

Main objective

To assess the efficacy of a comprehensive and specific training protocol focused on female players with DKV in preventing ACL injuries.

Specific objectives

1. To investigate the effects of a specific protocol as a preventive method of ACL injuries on the physical performance of female football players.
2. To analyze the injury incidence of ACL among players with DKV in both groups.
3. Check the changes in the neuromuscular control of the knee measured with the "*drop vertical jump test*" (DVJ) in both groups after the corresponding training proposal.
4. To evaluate the biomechanics of landing with jump landing measured with the landing error scoring system (LESS) in participants in both groups.

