5. To analyze the perceived satisfaction rates of the athletes, using the SF-12 questionnaire after the intervention.
6. Know the effective dosage of a specific protocol for the prevention of ACL injuries.

PICO Question

In soccer players with DKV... Does a specific training protocol reduce the risk of ACL injuries compared to the conventional program?

Study hypothesis

A comprehensive and specific 12-week training protocol for the 2023-2024 season will significantly reduce the risk of ACL injuries compared to conventional training for female soccer players with DKV.

METHODOLOGY

Ethical documents and prior registration

This study has the Authorization of the Ethics Committee of the Responsible Research Office of the Miguel Hernández University of Elche for the 2022/2023 academic year and will be registered as a clinical trial in the clinicalTrials platform.

Studio Design

The study is designed as a randomized and controlled, double-blind, unicentric and parallel group clinical trial protocol that will be carried out with the female players of Elche CF and Intercity CF in the province of Alicante. The recommendations of the SPIRIT guide³⁶ have been followed for the realization of this study. Annex I.

Before starting the study, they will be provided with a written informed consent that they must sign to record their intention to participate in it, being able to revoke it at any time and accepting the conditions that will appear in the document (Annex II). They will be randomly assigned to a conventional fitness training program or a specific training protocol for 12 weeks. This study will consist of 3 time measurement points, the first prior to the intervention, the second at the end of the 6-week period of intervention and the last at 4 weeks after its completion. The study schedule and flowchart are in Annex III and IV, respectively.

Participants

The recruited population will be formed by the 44 elite players (22 per team) with a federative record belonging to the first senior team of Elche CF and Intercity CF of the province of Alicante of the national women's football league during the 2023-2024 season, where three weekly training sessions of one hour each are carried out. Prior to the collection of data, permission will be requested from the Club and the coach of both teams to carry out the study at the Martínez Valero Stadium in Elche. In the same way,

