the recruitment will be carried out through a direct contact, as an interview, with the coach, the physiotherapist and the physical trainer of the participating teams.

Inclusion and exclusion criteria

The inclusion criteria will be:

- Football players registered and federated in the corresponding team.
- With an age range between 18 and 35 years.
- Minimum experience of one year playing football.
- With the presence of DKV.

The exclusion criteria will be:

- Previously injured subjects of ACL or other knee ligament injury.
- Subjects with a history of lower extremity injuries that have resulted in surgery during the six months prior to the study.
- Players with chronic illnesses that may affect test results.
- Subjects who practice other sports in the professional field.

Study variables and measurements

To record the number of injuries produced among the players of both groups at the end of the study and the frequency of weekly training, an Excel table will be used. The kinetics and kinematics of the lower extremities will also be analyzed with a motion capture system, surface EMG markers and a force platform. The LESS scoring system (Annex V) and the DVJ task will be used to identify the risk of injury during the jump-landing task and the presence of DKV among the players, respectively. In addition, we will measure their pre- and post-intervention satisfaction rates using the SF-12 questionnaire³⁸. Annex VI.

Sample size

An analysis was performed with Epidat 4.2 software to calculate the sample size required in the present study. A comparison of independent means will be performed and a standardized mean difference of 1, a significance level of 0.05, a 95% CI and a power of 90% will be considered, which determines a total sample size of 44 subjects, 22 in each group. It is necessary to consider an abandonment rate, so we will increase the sample by 10%. Therefore, the total sample size will be 48 women, 24 in each study group. Annex VII.

Randomization and blinding

Teams will be randomly assigned to one of the two groups in a simple manner and will be performed once subject selection has been completed. This assignment will be hidden and will be carried out by a person independent of the study. The randomization method will consist of the toss of a coin assigning "heads" to the intervention group and "tails" to the control group.

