First, an invitation will be made to all the players who are part of the teams mentioned above during the 2023-2024 preseason with the aim of starting the intervention during that same season. All respondents will receive a Google survey via WhatsApp. This questionnaire will include questions about the inclusion and exclusion criteria to select the study sample of interest as well as questions about their sports background (position, dominant limb and sports experience); anthropometric measurements (age, height, BMI and weight), which will be provided by the coaches of the selected teams; and aspects related to training (frequency of weekly training and rest period). After completing the survey, three weeks prior to the start of the clinical trial, all players who agree to participate must undergo a final screening to be included in the study. This screening will consist of undergoing a qualitative analysis of the DVJ (Annex VIII), so that, through a simple visual examination, the inclusion of those players who do not present DKV can be ruled out and only those who test positive for DKV can be registered. After selecting the final number of players, a joint talk will be given to both teams to expose the dynamics of the study and the confidentiality of the data. Subsequently, pre-intervention measurements will be carried out by the evaluating physiotherapists to record the initial state of the players. These measures will be: the quantitative analysis of the DVJ, the LESS score, the initial score in the SF-12 scale, the biomechanics of the lower extremities, the muscular activation of the lumbo-pelvic complex and the lower extremity.

During the 12 weeks that the intervention will last, periodic measurements will be made. The last one will take place one month after the end of it. In addition, the players will be asked to refrain from consuming performance stimulants, tobacco or alcohol, non-steroidal anti-inflammatory drugs (NSAIDs) or analgesics 24 hours before each session, as well as strenuous exercise. As a reminder, a WhatsApp will be sent to each athlete the day before each session, indicating the time at which they will be scheduled for training the next day. The appearance of pain during the sessions will not be allowed and, if at any time it appears, the training of the player in question will be stopped immediately and recorded for further analysis.

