The intervention will consist of performing 3 weekly training sessions for 12 weeks to reach a total of 36 sessions of 30-60 minutes each. The days that will be set for training will be Mondays, Wednesdays and Fridays, leaving a rest day between sessions to ensure adequate recovery and quality training. The physical trainers will have to agree so that the training load in both groups is very similar.

Next, we will proceed to detail the intervention that will be carried out in each of the two groups of this clinical trial:

Conventional fitness training group

The players who belong to this group will maintain the usual practice of football training, so no new intervention will be applied.

Training group with a specific ACL injury prevention protocol

This protocol is based on prevention programs that use a multifaceted approach, effective in reducing the risk of ACL injuries compared to those who used only one type of exercise^{14,21,34}. A wide variety of studies defend the importance of working the muscles of the trunk, hip and knee to prevent DKV^{23,28,30}. Therefore, lumbo-pelvic stabilization training (*core* stability) that includes motor stability and strengthening of the gluteal muscles, in addition to strengthening the lower limb itself, will lead to a significant improvement in neuromuscular control of the lower extremities and trunk in addition to producing a significant decrease in DKV and valgus moments^{10,18,20,24,29,30,32}.

The proposed exercise protocol will be designed taking into account the inclusion of three main components. Annex IX:

- Lumbo-pelvic stabilization exercises.
- Lower limb strengthening exercises.
- Integration exercises (plyometrics and balance).

The exercises integrated into the programme will be organised into three phases of implementation:

- **Phase 1** (adaptation - 1st month): Its objective is that the players learn and integrate new patterns while they train.
- **Phase 2** (Proficiency - 2nd month): Aims for players to master new patterns in a controlled environment.
- **Phase 3** (performance - 3rd month): Its objective is to perform exercises in situations as specific as possible and close to the demand and explosiveness of movements typical of the pitch.

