This clinical trial protocol seeks to encourage coaches of women's soccer teams to follow this type of program because of its potential benefits in preventing ACL injuries. Annex X. Almost all the studies reviewed confirm that there are varied prevention programs (plyometrics, balance, strength, among others) that provide a significant improvement in DKV and, therefore, in the prevention of ACL injuries, but none of them has been based on a standard dosage or applied specifically to female footballers in this age range who have the highest injury rate^{5,14,19,21,34}. On the other hand, studies such as Willadsen et al.³¹ report short-term benefits and intervention programs that do not exceed 6-8 weeks of training¹⁴. The purpose of this study is to implement a standardized protocol for a period of 12 weeks (longer intervention time) in players of senior women's teams with the aim of achieving long-term benefits.

Limitations

- The study will be carried out only with female footballers of a specific age range, so that, when extrapolating the results, data such as the prevalence of ACL injuries could not be generalized to the entire population, so it would reduce external validity.
- We would not have all the control over the execution of the exercises described in the protocol, since the physiotherapists in charge of giving instructions would not be constantly controlling how each player performs the exercises, only at the beginning of the program or when introducing new exercises.

- To properly quantify the load, it might be more appropriate to do so with an accelerometer. It would serve to better control the exercise since, when the speed decreased, it would be indicative of stopping the exercise.
- As in almost any study, there is a risk of abandonment of the subjects, which increases with the duration of the study. Being a 12-week intervention, dropout rates could be higher.
- The relationship of the menstrual cycle in female footballers could be considered throughout the protocol, since there could be alterations in the performance and execution of the exercises¹¹.

Strengths

- Observer bias will be mitigated because measurements will be performed by two different physiotherapists. Both will not know the results of the other measurements made to prevent their expectations from influencing the result.

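### The injury count has no dated window and appears to stop about four weeks after the programme, too soon to show the long-term benefit the protocol aims for

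*Combined protocol and SAP*

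**What the plan says.** Preventing ACL injury is the main objective, and ACL incidence in both groups is specific objective 2. Neither carries a time window. The Study hypothesis reads: "A comprehensive and specific 12-week training protocol for the 2023-2024 season will significantly reduce the risk of ACL injuries".

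The injury record is described once, under Study variables and measurements. An Excel table is to be used "To record the number of injuries produced among the players of both groups at the end of the study", together with the frequency of weekly training. No closing date is given.

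The end of the study has to be inferred from the measurement schedule:
- The Intervention section describes "performing 3 weekly training sessions for 12 weeks to reach a total of 36 sessions of 30-60 minutes each". Of the measurements it says: "The last one will take place one month after the end of it".
- The design section (headed Studio Design) lists three time points. The first precedes the intervention; the others are "the second at the end of the 6-week period of intervention and the last at 4 weeks after its completion".
- Players are invited "during the 2023-2024 preseason with the aim of starting the intervention during that same season". No start date is given.

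The long-term question appears twice. The Justification says of existing programmes: "These preventive programs are effective in the short term, but it is not equally confirmed whether they produce positive effects in the long term". The section on future expectations contrasts this trial's 12 weeks with shorter programmes and gives its purpose as "with the aim of achieving long-term benefits".

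**The concern.** A trial that cites the lack of long-term evidence as a reason to be done should observe its main outcome for some time after training stops. Here only about four weeks after the programme appear to be covered, and no injury surveillance beyond the last visit is described. A longer programme is not a longer follow-up: twelve weeks of training followed by four weeks of observation say nothing about whether protection persists. The Limitations list does not mention this.

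Two things are at stake. A statement about long-term benefit would have no data behind it. And few ACL injuries can be expected in 44 players, so any part of the season left unrecorded reduces an already small number of events. An undated window also leaves the closing date of the count open to choice once injuries are known.

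**Working it through.** **1. When the count ends.** With the 12-week programme of the Intervention section and a last measurement about four weeks later, 12 + 4 = week 16. The design section mentions a 6-week intervention period. If its last time point is counted from there, 6 + 4 = week 10. If week 6 is only a mid-programme visit, the end is again week 16. The passages must be reconciled; week 16 is used below.

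**2. The plan's own figure.** The Sample size section compares two means with standardized difference 1, two-sided alpha 0.05 and power 90%:

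n per arm = 2 × (1.960 + 1.282)² / 1² = 21.0, rounded up to 22, so 44 in total.

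This reproduces the stated 44. It does not involve injuries or follow-up time, so it gives no support to any injury window.

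**3. Share of the season not observed.** Season length S, in weeks from the start of the intervention, is an assumption. Unobserved share = 1 − 16/S.

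| S (weeks) | 26 | 30 | 32 | 36 | 40 | 44 |
|---|---|---|---|---|---|---|
| Unobserved | 38% | 47% | 50% | 56% | 60% | 64% |

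On the week-10 reading the range would be 62% (S = 26) to 77% (S = 44).

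**4. Expected ACL injuries.** From the documents: 3 training hours a week (Participants); 1.1 to 3.1 injuries per 1000 training hours, 12.6 to 23.6 per 1000 match hours, and a 16% to 32% share (Introduction); a 51% reduction (Justification). Assumed: one 90-minute match per team per week with 11 of 22 players on the pitch, and the 16% to 32% read as the ACL share of all injuries.

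Hours per player are 3 × 16 = 48 training and 1.5 × 0.5 × 16 = 12 match to week 16, and 120 and 30 to week 40.

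- Week 16, low: (1.1 × 48 + 12.6 × 12)/1000 = 0.204 injuries per player; × 0.16 = 0.0326 ACL injuries.
- Week 16, high: (3.1 × 48 + 23.6 × 12)/1000 = 0.432; × 0.32 = 0.138.
- Week 40, low and high: 0.510 × 0.16 = 0.0816 and 1.080 × 0.32 = 0.346.

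With the 51% reduction in one arm, the total is 22 × (1 + 0.49) × the per-player figure: 1.1 to 4.5 by week 16 and 2.7 to 11.3 by week 40. With no programme effect (× 44) it is 1.4 to 6.1 and 3.6 to 15.2. Either way the count rises by 40/16 = 2.5.

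Match play supplies most of these injuries: 151.2/204.0 = 74% at the low rates and 283.2/432.0 = 66% at the high rates.

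**5. Power for an injury comparison.** Fisher's exact test, 22 per arm, probability of injury = 1 − exp(−per-player figure). With no injuries in one arm, the other needs at least 5 (5 against 0 gives p = 0.048; 4 against 0 gives p = 0.108). Power for a 51% reduction is 0.04% to 4% at week 16 and about 1% to 12% at week 40, or up to about 17% if every player played every match in full. At week 40, 90% power would need 195 to 756 players per arm.

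**The case against.** Several points on the other side stand.
- Long-term benefit is not among the listed objectives. It is an aim in the section on future expectations, tied there to a longer programme than the 6 to 8 weeks used elsewhere. The same gap is nevertheless part of the Justification, and readers will expect the trial to address it.
- Week 16 is an inference. The study schedule is in Annex III, which is not in the text available here, so later surveillance cannot be wholly excluded.
- The event counts are generous. The Introduction's 16% to 32% follows sentences on knee injuries as well as ACL injuries. The upper figure of 15.2 is about 35% of 44 players (15.2/44). The counts are useful for the ratio between windows, not as forecasts.
- Extending the count is not free. The table as described holds injuries and training frequency, not match hours, and the Limitations note that abandonment grows with study duration.
- The gain is limited. Power stays low, and because whole teams are assigned by coin toss, one club is the intervention group and the other the control. No length of follow-up separates programme from club.

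These points lower the importance of the matter. None of them lets four weeks of observation after the programme support a long-term claim.

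**Conclusion.** The point holds as an inexpensive improvement rather than a fatal flaw. The injury count has no dated window. The end that the documents best support is about four weeks after the programme, and that cannot show long-term benefit. This conclusion needs no assumption about season length.

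Two stronger readings are tempting but not supported. A reader might infer that most of the time at risk is thrown away. That is true only if the season runs more than 32 weeks from the start of the intervention, which the documents do not say; the range is 38% to 64% for assumed seasons of 26 to 44 weeks. The later time is also simply not collected, rather than collected and discarded. A reader might also infer that the hypothesis promises season-long observation. Its wording attaches the season to the 12-week training protocol and sets no window for injury risk, so a 16-week count does not contradict it.

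Counting to season end would multiply exposure by S/16, or 2.5 at an assumed 40 weeks. It would not make 44 players enough for an ACL injury comparison.

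**What to change.** - State the start and end dates of the injury window, and reconcile the 6-week wording in the design section with the 12 weeks in the Intervention section.
- Keep the injury table running in both clubs to the end of the 2023-2024 season, without extra visits. Add training and match hours per player, and the date on which any player leaves.
- Report ACL injuries per exposure hour with a confidence interval to week 16 and, separately, to season end. Present both as descriptive, noting that the interval does not cover differences between clubs.
- Record whether and when the control club takes up the programme.
- Limit DVJ, LESS and EMG conclusions to four weeks after the programme, and remove long-term benefit as an aim for those outcomes.

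The cost is later final reporting, additional data entry by club staff (match hours in particular), and possible contamination if the control club adopts the programme. Reporting week 16 separately means that nothing in the present plan is lost. If the extension is refused, the window should still be dated and the long-term aim withdrawn for injuries as well.

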The study will have two physiotherapist evaluators, with at least five years of clinical experience. They will be responsible for the collection and analysis of data, assessments and evaluation of the final results. There will also be two sports physiotherapists, with at least five years of experience in the sports field, who will be responsible for the explanation and supervision of the exercises, in addition to being knowledgeable about the execution of specific training protocols.

A double-blind masking will be carried out, in which the evaluating physiotherapists and the players themselves will be blinded. Sports physiotherapists will be the only professionals who will not be. In addition, interventions and measurements will be performed in separate rooms, which will facilitate the blinding of subjects and evaluators.

Intervention

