During the execution of all the exercises, verbal and visual inputs will be received, such as the presence of a full-body mirror so that they can correct positions and verbal indications focused on lumbo-pelvic stability and the biomechanics of the lower limb to improve the concentration and motivation of the players during the execution of the scheduled exercises^{9, 12,17,21,33}.

The progression of the exercises will be established by increasing the speed of execution of the same, increasing the complexity of the task to be performed and by promoting neurocognitive implications (for example, counting backwards from 10 to 0 during the execution of the exercises). In addition, compliance with the proposed protocol will be verified through weekly self-reported questionnaires that will be sent via WhatsApp and will be part of the records to be analyzed later by the evaluators.

Expected results

The results we expect to obtain from the intervention group are directly related to the modification of risk factors such as DKV and the decrease in the injury incidence of ACL. It is expected to improve proprioception, body balance and motor control, not only of the lower extremities, but of the entire lumbo-pelvic complex. In addition, it is expected to improve sports performance and ball control on the pitch.

All changes that occur between the players in the intervention group will be measured and recorded. Changes in the neuromuscular control of the knee and the mechanical behavior of the joints proximal and distal to it^{23,28} will be analyzed with a jump-landing test (DVJ)^{19,27,28,32}. Taking advantage of the

previous test, the biomechanics of the jump landing will be evaluated and the risk of non-contact injuries will be identified using the LESS scoring system. In addition, during the execution of the DVJ, the data obtained from the activation of the different pre- and post-intervention muscle groups will be collected and processed with an EMG system^{19,27,29,30}. All these positive changes would imply a lower incidence of injury for the players in the intervention group, as well as higher levels of satisfaction compared to the control group.

Statistical analysis

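### Two blinded evaluators guard against expectation bias, but nothing in the available text stops a difference in their scoring level from entering the arm or time contrast, mainly on LESS

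*Combined protocol and SAP*

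**What the plan says.** In the combined protocol and SAP, the Randomization and blinding section sets up the measurement team: "The study will have two physiotherapist evaluators, with at least five years of clinical experience". Of these two it says: "They will be responsible for the collection and analysis of data, assessments and evaluation of the final results". It also states: "A double-blind masking will be carried out, in which the evaluating physiotherapists and the players themselves will be blinded". The same section fixes the unit of allocation: "Teams will be randomly assigned to one of the two groups in a simple manner". The method is a coin toss between two clubs, so each arm is one club.

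The Studio Design section sets the visits: "This study will consist of 3 time measurement points, the first prior to the intervention". The Intervention section lists what the evaluators record at baseline, including the quantitative DVJ and the LESS score. The Expected results section gives LESS a central role, saying that "the risk of non-contact injuries will be identified using the LESS scoring system".

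Under Strengths, the plan claims: "Observer bias will be mitigated because measurements will be performed by two different physiotherapists". The next sentence gives the mechanism: "Both will not know the results of the other measurements made to prevent their expectations from influencing the result".

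The available text does not say:
- which evaluator measures which player;
- whether a player keeps the same evaluator across visits;
- whether both evaluators score every player and, if so, how the two scores are combined;
- how the evaluators are spread over the two clubs.

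It describes no rater training and no agreement check. The Statistical analysis section has no evaluator term and does not say whether post-intervention scores or changes are compared.

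**The concern.** Having two observers does not in itself protect against observer error. It helps if both score each player and the scores are combined, or if the observers are spread evenly over the arms. Blinding and ignorance of other results stop an evaluator from scoring towards what she expects. They do not stop one evaluator from being stricter than the other, and a fully blinded rater can still be strict. The Budget estimate section says that the physiotherapists will be chosen from several clinics, so shared scoring habits cannot be presumed.

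This trial is more exposed than an individually randomized one. Because each arm is one club, an evaluator who follows a club also follows an arm, and an evaluator term in the model could then not be separated from treatment. If the evaluators instead change between visits, their difference appears as change over time, or as a group-by-time effect when the change differs by club. At stake is whether a difference on LESS can be read as an effect of the training programme.

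**Working it through.** **Inputs from the documents.** The Sample size section gives a standardized mean difference of 1, significance level 0.05, power 90%, and 44 players (22 per group). The Statistical analysis section makes the test two-sided, with ANOVA or Mann-Whitney. Arms coincide with clubs, and there are two evaluators.

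**Input assumed.** Let b be the systematic difference between the evaluators, in outcome SDs. The documents give no value. I take 0.1 to 0.5 as a range, without evidence that it applies to these evaluators.

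**Step 1: the plan's own figure.** n per group = 2(z₀.₉₇₅ + z₀.₉₀)² / SMD² = 2(1.960 + 1.282)² / 1² ≈ 21.0, rounded up to 22, so 44 in total. This reproduces the plan. Power from the noncentral t distribution at 22 per group is 89.97%.

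**Step 2: bias from an uneven split.** Let s be the difference between clubs in the share of players seen by the first evaluator. The bias in a comparison of post-intervention means is b × s. It is b when each evaluator takes one club (s = 1), half of b when s = 0.5, and zero when the shares are equal.

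**Step 3: consequence when s = 1, post-intervention scores only.** Rejection probabilities come from the noncentral t distribution with 42 degrees of freedom and noncentrality Δ√(22/2) = 3.317Δ. For the false-positive rate Δ = b. For power when the offset runs against a true effect of 1 SD, Δ = 1 − b.

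| b (SD, assumed) | False-positive rate (nominal 5%) | Power if the offset opposes a true SMD of 1 (90% without it) |
|---|---|---|
| 0.1 | 6.2% | 83% |
| 0.2 | 9.9% | 74% |
| 0.3 | 16.3% | 62% |
| 0.5 | 36.7% | 37% |

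With s = 0.5, the bias for b = 0.2, 0.3 and 0.5 is 0.10, 0.15 and 0.25 SD. The first of these corresponds to about 6% false positives.

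**Step 4: change from baseline.** If the same evaluator measures a player at every visit and the offset is constant, follow-up and baseline both carry it, so the change carries b − b = 0. Using baseline as a covariate with slope β leaves b × s × (1 − β), so it removes the offset only in part when the split is uneven. If the evaluators swap between visits, a shift of up to b enters the change.

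**Step 5: both evaluators score everyone.** If the two scores are averaged, both arms carry the same mean offset and the contrast between arms is unaffected.

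**Step 6: cost of a balanced rota.** With half of each club per evaluator, s = 0 and the type I error stays at 5%. Leaving the evaluator out of the model then adds only b²/4 to the variance, so the effective SMD is 1/√(1 + b²/4). Power is 89.7%, 89.3% and 88.2% for b = 0.2, 0.3 and 0.5. The sample size does not need to change.

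**The case against.** The strongest reply is that the Strengths item is about expectation, as its second sentence shows. Blinded evaluators and separate rooms for training and measurement support it. That stands: the item is not empty, and it should be faulted only for saying nothing about scoring level. Whether the blinding can be achieved is a different question.

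Three stronger readings are tempting, and the documents do not support them.

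- **That each evaluator will take one club.** No section says so. A single venue is named for both teams, and the Strengths item can equally mean that both evaluators measure every player, each unaware of the other's result. On that reading only a rule for combining the scores is missing.
- **That no later analysis could remove the offset.** Step 4 shows that it cancels in change from baseline when players keep their evaluator. Baseline LESS and DVJ are recorded, and the DVJ objective is worded as change. The percentages in Step 3 therefore describe a comparison of post-intervention scores only. The plan guarantees neither an analysis of change nor a constant evaluator.
- **That DVJ is as exposed as LESS.** The DVJ outcome is the quantitative analysis, and the Study variables and measurements section describes motion capture, surface EMG and a force platform. The visual DVJ examination in the Intervention section is an eligibility screen, not an outcome.

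It is also fair to say that the size of the offset is assumed, that the main objective is ACL injury rather than LESS, and that the annexes on the schedule, LESS and DVJ are not in the available text, so a rule there cannot be excluded. These points limit the weight of the concern. They do not fill the gap in the main text.

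**Conclusion.** The concern holds as a conditional one. The stated safeguards deal with expectation bias and leave a difference in scoring level between the evaluators uncontrolled. If the evaluators are split by club or change between visits, that difference can pass for a treatment or time effect, chiefly on LESS and probably much less on DVJ.

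The rates of about 10%, 16% and 37% rest on three assumptions: one evaluator per club, post-intervention scores only, and offsets of 0.2, 0.3 or 0.5 SD that the documents do not supply. Harm is possible, not demonstrated.

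The plan should still be changed before baseline measurements, because the remedy lies in how the data are collected. Once evaluators have followed clubs or swapped between visits, the analysis may be unable to make up for it fully. The confounding of club with arm is a separate and larger problem, which balancing the evaluators does not touch.

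**What to change.** In Randomization and blinding, state that each evaluator assesses half of the players of each club, and that every player keeps the same evaluator at all three time points, with earlier scores withheld from the evaluator.

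For LESS, have both existing evaluators score every trial independently, take the mean as the outcome, and report their agreement. The rota then matters mainly for the other measurements.

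Record which evaluator made each measurement. In Statistical analysis, state that LESS is analysed with its baseline value. With a balanced rota, change and covariate adjustment are both free of the evaluator bias; without one, only change with a constant evaluator removes a fixed offset completely.

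Reword the Strengths item to claim only these protections. If an annex already holds an assignment or scoring rule, cite it in the main text and check that it meets these conditions.

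The cost is a rota, some extra scoring time for LESS, and a small risk that an evaluator who sees the same player again recalls her earlier scores. No new staff and no increase in sample size are needed.
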